3. TRIAL DESIGN

PICCOLO is a multi-centre, open-label, randomised, controlled, 4 arm clinical trial designed to show whether, regardless of tumour subtype, the novel regimen **IrCs**, is non-inferior for anti-cancer efficacy and superior for toxicity compared to **Ir**, and whether, in patients with *K-RAS* wild-type tumours, the addition of panitumumab to irinotecan, **IrPan**, gives superior anti-cancer efficacy compared to **Ir** alone.

Potential PICCOLO patients are invited to consent to retrieval of stored tumour samples to test for *K-RAS* mutations at codons 12, 13 and 61. Thereafter, patients who fulfil the eligibility criteria and give informed consent are randomised according to their tumour *K-RAS* status as shown in the flow diagram on page 5.

Patients whose tumours are shown to have a mutation in *K-RAS*, and those in whom *K-RAS* genotyping is not possible due to assay failure or unavailability of tissue, are allocated on a 1:1 random basis to receive **Ir** or **IrCs**. This randomisation uses the minimisation factors listed in the flow diagram.

Patients whose tumours are wild-type for *K-RAS* are allocated on a 1:1 random basis to receive **Ir** or **IrPan**. This randomisation is stratified according to whether or not the patient has received prior anti-EGFR targeted therapy (e.g. cetuximab or panitumumab), and uses the minimisation factors listed in the flow diagram.

Recruitment to PICCOLO will continue until 480 non-EGFR-pre-treated *K-RAS* wild-type patients have entered the **Ir** vs. **IrPan** randomisation (240 patients per arm), and 750 patients have entered the **Ir** vs. **IrCs** randomisation (375 patients per arm). The **Ir** vs. **IrPan** comparison includes approximately 143 patients fulfilling these criteria who were randomly allocated to **Ir** or **IrPan** under Protocol Version 1 (in whom *K-RAS* status is being determined retrospectively), plus approximately 337 patients to be recruited using Protocol Version 2. The **Ir** vs. **IrCs** comparison includes 329 patients randomly allocated to **Ir** or **IrCs** under Protocol Version 1 (regardless of their *K-RAS* status), plus approximately 421 patients to be recruited using Protocol Version 2. The recruitment ratio to the **Ir** vs. **IrCs** comparison and the **Ir** vs. **IrPan** comparison is dependent upon the proportion of patients with unknown *K-RAS* status (which we

anticipate to be around 15%). This will be monitored throughout the study as this may vary. In order to achieve the required number of patients for each comparison we will recruit approximately 1324 patients in total (494 already recruited under Protocol Version 1; 830 using Protocol Version 2, assuming 15% of patients with unknown *K-RAS* status, and 15% of patients have previously received anti-EGFR targeted therapy).

Patients randomised using the previous version of the protocol, without advance knowledge of *K-RAS* status, will have their *K-RAS* status determined retrospectively (provided consent has been obtained for tissue retrieval), and will be incorporated in the relevant treatment comparisons as detailed in Section 11.

In addition, approximately 86 anti-EGFR targeted therapy pre-treated patients who have wild-type *K-RAS* status will be available for an assessment of the efficacy of **Ir** versus **IrPan** in this pre-treated group. Similarly, patients randomised to Ir or IrPan using the previous version of the protocol, who are retrospectively found to have mutant or unknown *K-RAS* status, will be available for an assessment of the efficacy of **Ir** versus **IrPan** in this group of patients

All PICCOLO patients are studied for clinical and pharmacogenetic endpoints. All patients are also invited to donate any surplus stored formalin-fixed paraffin-embedded (FFPE) tumour samples for translational research. A pharmacokinetic (PK) Sub-study is being undertaken in 20 patients randomised to IrCs at centres with appropriate facilities in order to compare Ir, SN38 and SN38G pharmacokinetics after Ir or IrCs treatment.

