11. STATISTICAL CONSIDERATIONS

11.1 Sample Size

Ir vs IrCs comparison

A non-inferiority design is proposed, based upon the proportion of patients progression-free at 12 weeks from randomisation. In a previous study in a similar patient population receiving irinotecan, median PFS was 4.2 months, with 63.3% of patients progression-free at 12 weeks.³⁸ There are no previous best supportive care (BSC) trials that have included regular CT scan assessments, however in a trial comparing irinotecan with BSC, at the time point that 63% of Ir

patients were alive, less than 40% of BSC patients were alive⁴⁰. On this basis we have estimated that a similar proportion – 40% - of patients on BSC would be expected to be progression-free at 12 weeks applying standard WHO or RECIST criteria. On this basis irinotecan contributes at least 23% to the proportion of patients progression-free at 12 weeks. On the basis of clinician consensus IrCs will be defined as no worse than Ir if median PFS is at least 3 months with IrCs, equivalent to at least 52.7% of patients in the IrCs arm progression-free at 12 weeks. This corresponds to a reduction of no more than 10.6% in the proportion of patients progression-free at 12 weeks which is our non-inferiority margin; retaining more than half the effect that irinotecan has over BSC. The sample size calculation for the Ir vs. IrCs comparison remains the same since there is no data to suggest that *K-RAS* status is a predictive factor for Irinotecan or Ciclosporin.

We will conduct a one-sided test for non-inferiority.³⁹ With 80% power and a significance level of 2.5%, 680 patients are required to test for this degree of non-inferiority using a one-sided chi-squared test without continuity correction. To account for a 10% drop-out or 5% cross-over, 750 patients (375 per arm) would need to be randomised in total. This sample size also gives over 90% power for claiming non-inferiority of PFS using a one-sided modified log-rank test with significance level 2.5% (at least 273 PFS events are required to assess non-inferiority with 80% power), and allows detection of a clinically relevant relative reduction of 50% (from 20% with Ir to 10% with IrCs) in the proportion of patients experiencing grade 3+ diarrhoea within 12 weeks of randomisation, with over 90% power and at a 5% (two-sided) significance level, using a two-sided chi-squared test without continuity correction.

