Since previous anti-EGFR targeted therapy use is of no concern for the Ir vs. IrCs comparison, this analysis will include all patients randomised to receive either Ir or IrCs under Protocol Version 1.0, and all patients randomised to receive either Ir or IrCs via the Ir vs. IrCs randomisation in this amended protocol, regardless whether or not they have previously used anti-EGFR targeted therapy.

The two primary comparisons of Ir vs. IrCs and Ir vs. IrPan are essentially two independent comparisons⁴¹. We therefore aim to recruit 480 patients who have wild-type *K-RAS* status and who have not previously received an anti-EGFR targeted therapy (240 patients per arm) to the Ir vs. IrPan comparison. However, dependent upon the proportion of patients with unknown *K-RAS* status, there may be some over-recruitment to this comparison. We expect approximately 15% of all patients recruited to this comparison to have previously received an anti-EGFR targeted therapy therefore the expected sample size for the exploratory analysis of Ir vs. IrPan for those patients previously receiving an anti-EGFR targeted therapy (and who have wild-type *K-RAS* status) is approximately 86 patients (43 patients per arm of Ir/IrPan).

K-RAS status

We expect that the split between mutant *K-RAS* status and wild-type *K-RAS* status will be approximately 42:58, and that approximately 15% of patients will have unknown *K-RAS* status. The proportion of patients with unknown status will be monitored as this figure may vary. Only patients with wild-type *K-RAS* status will be randomised to the Ir vs. IrPan comparison. There will, however, be some patients randomised to IrPan via protocol Version 1.0 who will have either mutant or unknown *K-RAS* status. We anticipate that approximately 167 mutant or unknown *K-RAS* status patients will have been randomised to receive either Ir or IrPan under Protocol Version 1.0, of whom approximately 19 will have previously received an anti-EGFR targeted therapy. An exploratory analysis will be carried out on these patients.

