Analysis of 12-week assessments will include all patients assessed between 10 and 14 weeks from randomisation. A sensitivity analysis will be conducted to allow for patients assessed outside of this 2 week time frame. Analysis of response will be performed using the centrally reviewed outcome. If the centrally reviewed outcome is missing, the primary analysis will class the patient as being progression-free at 12 weeks (if alive), and a sensitivity analysis will be conducted using the outcome of the local assessment. If this is also missing, the patient will be classed as having progressed at 12 weeks in the sensitivity analysis.

A two-sided 5% significance level will be used for all superiority endpoints, and a one-sided 2.5% significance level will be used for all non-inferiority endpoints.

Safety data (adverse events and serious adverse events as detailed in Section 8) will be presented for all patients by treatment group and comparison, and by relationship to study drug, or underlying colorectal cancer.

Ir vs IrCs comparison

All patients randomised to receive either Ir or IrCs via protocol Version 1.0 or to the Ir vs. IrCs comparison under protocol Version 2.0 (i.e. mutant/unknown *K-RAS* status), regardless of previous anti-EGFR targeted therapy use, will be included in this comparison.

Primary Endpoint

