Should non-inferiority of IrCs to Ir be shown, we will consider both treatment groups together, and conduct exploratory subgroup analyses comparing patients' outcome according to the clinical minimisation factors and previous anti-EGFR targeted therapy use.

Ir vs IrPan comparison (patients with wild-type K-RAS status not previously receiving an anti-EGFR targeted therapy)

Patients with wild-type *K-RAS* status randomised via the 'no previous anti-EGFR targeted therapy use' randomisation will be included in this comparison.

Primary Endpoint

Overall survival curves will be calculated using the Kaplan Meier method and compared using a 2-sided log-rank test. OS will also be compared between the control and experimental groups using multivariate modelling. Cox's proportional hazards model, if appropriate, will be used to adjust for the minimisation factors and other important prognostic factors. HRs and corresponding 95% CIs for OS will be presented. Primary analysis will be based on the multivariate analysis which adjusts for the minimisation factors.

Secondary Endpoints

The difference in proportion of patients who are progression-free at 12 weeks from randomisation between treatment groups will be compared using a two-sided chi-squared test. Logistic regression will also be used to adjust for the minimisation factors and any other covariates identified to influence patients' prognosis. Treatment and covariate estimates with corresponding 95% CIs will be given. To account for any deaths from causes other than colorectal cancer which may occur within 12 weeks of randomisation, for patients who have no evidence of disease progression, sensitivity analyses will be conducted classifying these patients as progression-free (these patients will be classed as with progressive disease at 12

weeks in the main analysis). Sensitivity analysis will also be conducted to account for patients with missing data regarding progression at 12 weeks, using local assessment data or classifying these patients as with progressive disease, as appropriate.

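### Ir vs IrCs is framed as holding whatever the tumour subtype, but K-RAS wild-type patients are under-represented in it and no stated analysis estimates the effect by K-RAS status

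*Protocol*

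**What the plan says.** Section 3 describes a trial "designed to show whether, regardless of tumour subtype, the novel regimen" IrCs is non-inferior to Ir for efficacy and better for toxicity. The same section sends patients with mutant or undetermined K-RAS to Ir or IrCs, and wild-type patients to Ir or IrPan. Section 5.2 repeats this.

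The Ir vs IrCs comparison keeps its earlier recruits. Section 3 counts in it 329 people who had already joined one of these two arms "under Protocol Version 1 (regardless of their *K-RAS* status), plus approximately 421 patients to be recruited using Protocol Version 2". Section 12 defines the analysis set in the same way: "All patients randomised to receive either Ir or IrCs via protocol Version 1.0 or to the Ir vs. IrCs comparison under protocol Version 2.0", the latter group being glossed as "i.e. mutant/unknown *K-RAS* status), regardless of previous anti-EGFR targeted therapy use, will be included in this comparison".

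Section 11.1 says "The sample size calculation for the Ir vs. IrCs comparison remains the same", because no data suggest that K-RAS predicts the effect of irinotecan or ciclosporin. It expects that the split between mutant and wild-type "status will be approximately 42:58", with about 15% unknown.

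For analysis, section 12 bases the primary Ir vs IrCs result on a logistic model adjusted for the minimisation factors. Those listed in section 5.2 do not include K-RAS. A further model adds previous anti-EGFR therapy and any other covariates found to be prognostic. If non-inferiority is shown, the two arms are to be taken together to "conduct exploratory subgroup analyses comparing patients' outcome according to the clinical minimisation factors" and to previous anti-EGFR therapy.

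**The concern.** K-RAS status now decides who can enter this comparison, so the analysed sample no longer has the K-RAS mix of second-line patients in general. The stated aim still spans all tumour subtypes. Section 1 calls mutant K-RAS a marker of poor prognosis, yet K-RAS is named in neither the covariate list nor the subgroup list. Previous anti-EGFR therapy, which section 11.1 says is of no concern for this comparison, is named in both.

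The subgroup work that is stated merges Ir and IrCs. It can describe prognosis by factor, but it cannot say whether the IrCs effect varies with that factor.

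At stake is how far a non-inferiority result can be carried. It would be read as applying to wild-type patients, who are the majority of genotyped patients. For them the evidence would be thin, and the bridging assumption in section 11.1 would go unexamined although the trial holds data that bear on it.

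**Working it through.** **Inputs (protocol).** Control rate 63.3%, lowest acceptable IrCs rate 52.7%, margin 10.6 points, one-sided 2.5%, 80% power, 680 patients rising to 750 (section 11.1). 329 Version 1 and about 421 Version 2 patients (section 3). Mutant to wild-type 42:58 and 15% unknown (section 11.1).

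**1. The plan's own figures.** With the pooled-variance formula without continuity correction and mean rate (0.633 + 0.527)/2 = 0.58:

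n per arm = [1.96 × √(2 × 0.58 × 0.42) + 0.842 × √(0.633 × 0.367 + 0.527 × 0.473)]² / 0.106² ≈ 339.2, so 340, or 680 in total. This matches the protocol.

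The K-RAS assumptions also reproduce. The mutant or unknown share is 0.85 × 0.42 + 0.15 = 0.507, the stated 50.7%. For Version 1, 329 × 0.507 = 167, the mutant/unknown number that section 11.1 gives for Version 1 Ir/IrPan patients. The split is therefore reasonable for Version 1 Ir/IrCs patients too.

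**2. Expected make-up of the 750.**

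| K-RAS status | Version 1 | Version 2 | Total | Share |
|---|---|---|---|---|
| Known wild-type | 329 × 0.85 × 0.58 = 162 | 0 | 162 | 22% |
| Known mutant | 329 × 0.85 × 0.42 = 117 | 421 × 0.357/0.507 = 296 | 414 | 55% |
| Unknown | 329 × 0.15 = 49 | 421 × 0.15/0.507 = 125 | 174 | 23% |

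(Totals are from unrounded values.) If unknown status in Version 1 runs from 10% to 30%, known wild-type falls from 172 to 134 (23% to 18%).

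Unknown is a missing genotype, not a subtype. If 58% of unknowns are wild-type (an assumption), the true wild-type number is 329 × 0.58 + 125 × 0.58 ≈ 263, or 35% of 750, against 58% in an unselected population.

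**3. Precision in wild-type patients.** With 81 per arm and 63.3% in both arms:

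- SE = √(2 × 0.633 × 0.367/81) = 7.57 points
- 95% half-width = 1.96 × 7.57 = 14.8 points, wider than the 10.6-point margin
- Non-inferiority power = Φ(10.6/7.57 − 1.96) = Φ(−0.56) ≈ 29%

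Even if all 263 could be identified, the half-width would be about 11.7 points and power about 43%.

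**4. Precision of an interaction.** For the 414 known mutant patients (207 per arm), the half-width is 1.96 × √(2 × 0.633 × 0.367/207) = 9.3 points. The wild-type minus mutant contrast then has half-width √(14.8² + 9.3²) ≈ 17.5 points. It is estimable but imprecise.

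**5. What the stated analyses can show.** The primary model has no K-RAS term. The wider model could admit K-RAS as another prognostic covariate, but a main effect gives no treatment effect by subtype. The subgroup step merges the arms. None of these yields an IrCs minus Ir estimate by K-RAS status.

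**The case against.** The strongest reply has four parts.

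- **The phrase is modest.** It can be read simply as saying that the IrCs question is not restricted by K-RAS, in contrast to the IrPan question. Objective 1 and the endpoints promise no non-inferiority within each subtype. That reading is fair, but the sentence does not say so, and it stands where a reader looks for the scope of the claim.
- **The assumption is open and plausible.** Section 11.1 states it. Ciclosporin acts on host biliary excretion, the regimen was chosen to match systemic exposure, and a PK sub-study checks this. The documents give no reason to expect a K-RAS interaction. This stands, and it keeps the point modest.
- **The analysis plan may cover it.** It is not shown. Section 12 says that a finalised plan corresponding to Version 1.0 exists and that changes will be documented. An analysis by K-RAS may therefore exist. The point rests on what section 12 itself fixes.
- **A subgroup table cannot settle the matter.** True: it would be imprecise, so it can inform but not decide.

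Stronger readings are tempting and fail. A reader might infer that the claim has no support in wild-type patients; about 162 are in the comparison. A reader might infer that K-RAS is known for everyone pooled; retrospective testing depends on consent, assays fail, and about 174 of 750 are expected to be unknown. A reader might infer confounding; allocation between Ir and IrCs is equal under both versions, so the arms are comparable in expectation. A reader might also put a figure on how often a wild-type loss would be masked. That needs an effect the documents do not suggest, and it depends on the unknowns: a hypothetical 15-point loss pools to 15 × 162/750 = 3.2 points if no unknown patient shares it, and to 15 × 263/750 = 5.3 points if 58% do.

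**Conclusion.** The concern holds in a limited form. Wild-type patients are under-represented in Ir vs IrCs: about 22% known, or about 35% counting latent wild-type among the unknowns, against 58% naturally. For them the claim across subtypes is only weakly supported, with a half-width of about 14.8 points against a 10.6-point margin and about 29% stand-alone power. The analyses stated in section 12 do not examine whether the IrCs effect differs by K-RAS, so applying the result to wild-type patients rests on the assumption in section 11.1.

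This does not invalidate the primary analysis, and it is no evidence that IrCs performs worse in wild-type disease. The figures assume that 42:58 and 15% apply to the Version 1 Ir/IrCs patients, that untyped tumours share the 58% rate where stated, and that the true rate is 63.3% in both arms.

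**What to change.** - **Section 12, primary Ir vs IrCs model:** add K-RAS status (wild-type, mutant, unknown) as a covariate, stating that unknown denotes a missing genotype and not a subtype.
- **Section 12, exploratory analysis:** report the IrCs minus Ir difference in the 12-week progression-free proportion with 95% CI for each K-RAS group, plus a treatment-by-K-RAS interaction estimate. Keep the arms apart and label the results exploratory and imprecise.
- **Section 3:** limit the wording on tumour subtype to the K-RAS mix actually enrolled. State that applying the result to wild-type patients rests on the no-interaction assumption in section 11.1.

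The cost is one covariate, one table and a narrower sentence. K-RAS is already being determined, so no patients or tests are added. If the current analysis plan already contains this analysis, only the cross-reference and the section 3 wording remain to be changed.

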4. ELIGIBILITY

The eligibility criteria are designed to include, as far as possible, any patient for whom standard single-agent irinotecan would normally be a treatment option, in accordance with its marketing licence and current NICE guidance.

Patient Selection

The Cancer Diagnosis

- Confirmed advanced colorectal adenocarcinoma:
 - **either** previous or current histologically confirmed primary adenocarcinoma of colon or rectum, together with clinical/radiological evidence of advanced/metastatic disease
 - **or** histologically/cytologically confirmed metastatic adenocarcinoma, together with clinical/radiological evidence of colorectal primary tumour
- Unidimensionally measurable disease (RECIST criteria, see Appendix 1)
- Not known to have CNS metastases or carcinomatous meningitis

Previous Anticancer Treatment

- Patient must have had prior fluoropyrimidine +/- oxaliplatin therapy, with disease progression during or after that treatment:
 - adjuvant therapy and/or prior therapy for advanced disease may have been given.
 - if disease has progressed after but not during prior therapy, the treating consultant should be satisfied that further fluoropyrimidine (+/- oxaliplatin) therapy is not appropriate.

- if the only prior chemotherapy was given adjuvantly, progression should have occurred during or <3 months after completing the adjuvant course, and the treating consultant should be satisfied that further fluoropyrimidine (+/- oxaliplatin) therapy is not appropriate
- No previous treatment with irinotecan may have been given
- Prior anti-EGFR therapy (cetuximab; panitumumab) and/or bevacizumab is acceptable, but patients with a prior anaphylactic reaction to cetuximab should not be entered.
- Please note the minimum acceptable time intervals from the end of previous therapy to the planned start of PICCOLO treatment:
 - Capecitabine: 14 days
 - All other licensed cytotoxic drugs: 21 days
 - Prior cetuximab, panitumumab or bevacizumab: 21 days
 - Any experimental anticancer drug therapy including antibodies: 42 days
 Note also that PICCOLO treatment must start as soon as possible (maximum 14 days) after randomisation.
- Prior radical pelvic radiotherapy is not an absolute contraindication, however patients with ongoing radiotherapy toxicity, especially diarrhoea, should not be entered into PICCOLO.

Patient Fitness and Co-morbidity

- WHO performance status of 0, 1 or 2, with estimated life expectancy of at least 12 weeks
- Full blood count:
 - Hb ≥ 10.0 g/dl; WBC $\geq 3.0 \times 10^9/l$; Plts $\geq 100 \times 10^9/l$
- Renal biochemistry:
 - GFR calculated by the Cockcroft formula ≥ 50 ml/min, or measured GFR (EDTA or 24hr creatinine clearance) ≥ 60 ml/min.
- Hepatobiliary function:
 - ALP ≤ 5 x Upper Limit of Normal (ULN), and AST or ALT ≤ 2.5 x ULN
 - bilirubin ≤ 25 umol/l, and no clinical or radiological evidence of biliary obstruction
 - no known history of Gilbert's syndrome
- Medical comorbidity:
 - no ongoing requirement for for ciclosporin or a contraindicated concomitant medication (see section 6.6). Short-course antibiotics or antifungals are acceptable if they will finish > 5 days before start of PICCOLO therapy.
 - no concurrent or previous other cancer that could confuse diagnosis (non-melanomatous skin cancer or superficial bladder cancer acceptable; for other cases please discuss with CTRU)
 - no other serious medical condition: e.g.: major surgery within preceding four weeks, unresolved bowel obstruction; uncontrolled infection, uncontrolled chronic enteropathy (e.g. Crohn's disease, ulcerative colitis), or chronic diarrhoea (≥ 4 stools per day) of any cause
 - no clinical or radiological evidence of interstitial pneumonitis, pulmonary fibrosis, pleural effusion or ascites causing grade ≥ 2 dyspnea

Other Factors

- Aged ≥ 18 years
- Capable of oral self-medication, reporting toxicity and completing QoL questionnaires
- If female and of childbearing potential, must:
 - have a negative pregnancy test within 72 hours prior to trial entry, and not be breastfeeding

- agree to use adequate, medically approved, contraceptive precautions (oral or barrier contraceptive under the supervision of a General Practitioner or Family Planning Clinic) during and for 6 months after study treatment
- If male with a partner of childbearing potential, must:
 - agree to use adequate, medically approved, contraceptive precautions (oral or barrier contraceptive under the supervision of a General Practitioner or Family Planning Clinic) during and for 6 months after study treatment

